Revitalize Cognition: Near Infrared Stimulation in Older Adults

NCT06688357

11/13/2024

Updated Statistical Plan

Updated Statistical Analysis Plan

Due to the small N, we examined cognitive and emotion outcome variables using change scores (post intervention – baseline). These change scores were evaluated as a function of treatment group (active, sham) using independent t-tests. Cohen's D effect sizes were computed to guide selection of potential cognitive measures for use in future clinical trials, as appropriate.

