6.2 Participants

Participants will include individuals, age 62 years and older, who are independently living and willing to undergo a two-week intervention program. Our study groups will consist of the following: 70 cognitively normal individuals (N= 35/group), 20 individuals with amnestic MCI (N=10/group), 20 individuals with nonamnestic MCI (N=10/group), and 40 nondemented individuals with Parkinson disease (N=20/group). Based on our previous intervention studies with older adults, we anticipate a 20% attrition rate and up to 50 screen failures. To account for screening failures and study attrition, we anticipate consenting 206 individuals.

Informed Consent: Informed consent will be obtained according to university and federal guidelines. The informed consent process may begin with the initial telephone screening call, when a prospective participant is contacted or calls to find out more information about the study (See Telephone Script). After that first phone contact, the participant will be sent a copy of the Informed Consent via hardmail or via email if they are interested, and/or scheduled for an appointment in the VITAL laboratory or at the Fixel Center for Neurologic Diseases to discuss the study in more detail and in person.

Other potential participants, particularly those seen during the clinics of the PI or co-investigators, will be directly asked about their interest in this study and will be provided a copy of the informed consent to review.

During the first study visit, the project will be explained in more detail to the potential participant by the study coordinator or approved staff and the Informed Consent will be reviewed. Participants will be informed that this is a randomized trial and that there is 50% likelihood they may receive the sham intervention. The participant will be given the opportunity to ask questions. No study interventions will begin until the Informed Consent

(ICF) paperwork is signed. Participant will be given a signed copy of the ICF paperwork, and a copy will be kept on file with the Principal Investigator.

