7.2. Randomization and Statistical Methods

7.2.a. Randomization. Participants in the Cognitively Normal, the MCI, and Parkinson groups will be independently assigned to Sham and Treatment groups on a 1:1 ratio. For the Cognitively Normal group, we anticipate an N of 35 in each treatment group. For each MCI group, we anticipate an N of 10 per treatment group. For the PD group, we anticipate an N of 20 per treatment group. Randomization will be stratified according to age and MoCA/MMSE scores so as to prevent different average ages or cognitive status scores between the treatment groups. Treatment assignment will be pseudorandomized in order to have comparable distributions of age and cognitive screening scores across Sham and Treatment interventions. Procedures will be followed so that group assignments are not available to individuals administering and scoring baseline/pre-intervention and post-intervention cognitive/mood data.

7.2.b. Missingness and Intent to Treat.

All data will be checked for missingness, out-of-range values, and distributional form (i.e., normality, homogeneity of variance). Decisions regarding use of parametric vs. nonparametric statistics will be based on the results of those analyses. Standard summary statistics will be provided for pre- and post-stimulation. Intent to treat analysis will be used to reduce selective attrition bias; participants who are unwilling/unable to continue with intervention will be encouraged to attend the post intervention testing, if possible. Thus, statistical analyses will be performed on two data sets: 1) on all subjects who were successfully screened, randomized and able to participate in at least 1 week of the assigned intervention, regardless of study

completion (intention-to-treat analysis); and 2) on subjects who were successfully screened, randomized and able to complete at least 80% of the treatment assignment.

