7.3. Statistical Analyses

Data for each group (Cognitively Normal, MCI, Parkinson) will be analyzed separately. However the same analytic approach will be taken for each, as described below. Some analyses will be truncated for the MCI groups due to the smaller sample size.

Aim 1: Aim1 will test the hypothesis that individuals in the active stimulation group will show improved cognitive function compared to the sham group. Separate mixed model ANOVAs (2 [Group: Active Stimulation, Sham stimulation] x 2 [Occasion: Pre-testing, Post-testing]) will be conducted using the executive and Memory outcome variables. When significant, appropriate post-hoc analyses will be conducted. Additional analytic techniques will involve 'change score' analyses, as well as analyses examining predictors of changes (i.e., age, education, gender).

Aim 2: Aim 2 will test the hypothesis that individuals in the active stimulation group will show improved emotion/psychological function compared to the sham group. Separate mixed model ANOVAs (2 [Group: Active Stimulation, Sham stimulation] x 2 [Occasion: Pre-testing, Post-testing]) will be conducted using the mood outcome variables (mood modules NIH Toolbox, STAI, POMS, BDI-II). When significant, appropriate post-hoc analyses will be conducted. Additional analytic techniques will involve 'change score' analyses, as well as analyses examining predictors of changes (i.e., age, education, gender).

Aim 3: This neuroimaging aim is exploratory and will test the hypothesis NIR intervention will produce pre-post increases in frontal and temporal brain markers of MRS ATP function and pre-post increases in connectivity in frontal and medial temporal lobe mediated resting state brain networks (resting state fMRI). Although this aim will require extensive data reduction, the overall data analytic plan is similar to that of Aims 1 and 2.

Aim 4: This is aim is specific to Parkinson disease and will test the hypothesis that active NIR stimulation will result in greater pre-post intervention improvement in motor parameters (UPDRS, fine motor speed, gait, balance) than sham. Separate mixed model ANOVA's will be conducted similar to those described in Aims 1 and 2.

Finally, we plan to examine whether various 'factors' might potentially be moderators or mediators to intervention success. WE plan to examine age, education, gender, health comorbidities, processing speed and mood.

8. Methodological Limitations

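### The SAP's change-score t-tests leave out the outcome's own baseline score; a baseline-adjusted ANCOVA beside them would usually be more precise at moderate pre-post correlation, though not in every small cohort

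*SAP*

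**What the plan says.** The SAP is a single paragraph. It gives the reason and the outcome form, "Due to the small N, we examined cognitive and emotion outcome variables using change scores", then the test, "These change scores were evaluated as a function of treatment group (active, sham) using independent t-tests". It adds that Cohen's d "effect sizes were computed to guide selection of potential cognitive measures for use in future clinical trials". It does not state the SD behind d, the t-test version (pooled or Welch), the analysed N, or whether cohorts are kept apart.

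Protocol section 7.3 keeps them apart: "Data for each group (Cognitively Normal, MCI, Parkinson) will be analyzed separately". Its main model for Aims 1 and 2 is: "Separate mixed model ANOVAs (2 [Group: Active Stimulation, Sham stimulation] x 2 [Occasion: Pre-testing, Post-testing]) will be conducted". It also lists change scores as a further technique: "Additional analytic techniques will involve 'change score' analyses". Age, education and gender are named there as predictors of change, and section 6.6.5c names skin type as a covariate. The baseline value of the outcome being analysed is not named as a covariate in either document.

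**The concern.** Section 6.7.2 of the protocol says the study is kept short because its purpose is to gauge effect sizes and feasibility, and the SAP uses d to choose cognitive measures for later trials. The precision of each estimated effect is therefore much of what the analysis delivers.

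A change-score comparison subtracts the whole baseline score. When pre and post scores correlate only moderately, that is too much: an arm that starts lower by chance tends to appear to improve more. ANCOVA estimates the coefficient from the data and usually gives a tighter estimate at the cost of one degree of freedom. A small sample is not in itself a reason to leave out that one covariate.

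**Working it through.** **Inputs from the documents.** Planned n per arm is 35 (cognitively normal), 20 (Parkinson) and 10 (each MCI cohort), from Protocol section 6.2. The same section says "we anticipate a 20% attrition rate and up to 50 screen failures". If the 20% came out of those arms they would be 28, 16 and 8; section 6.2 can also be read as recruiting extra people to cover it. Retest correlations appear only for secondary mood scales (sections 6.6.4b to 6.6.4d): STAI 0.31 to 0.86, POMS 0.65 to 0.74, BDI-II 0.93. The plan states no power, SD or detectable effect, so there is no figure of its own to reproduce.

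**Assumptions.** r = 0.5 and 0.7 for illustration; 6 per arm as a low case for the unstated N; two-sided 0.05; a true effect of 0.5 baseline SD for power.

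**Step 1: relation to the planned model.** With complete pairs and a pooled variance, the group x occasion F equals the squared change-score t. On simulated arms of 9 and 13, F = 0.0375 on 20 df and pooled t² = 0.0375 (Welch t² = 0.0373). On arms of 6 and 8, F = 0.4778 and pooled t² = 0.4778, but Welch t² = 0.4110. The SAP's test therefore neither gains nor loses precision against the planned interaction, apart from the Welch version or missing post scores.

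**Step 2: variance, equal pre and post SD.** Let N = 2n be the cohort total.
- Change score: proportional to 2(1 − r).
- ANCOVA: proportional to (1 − r²) × (N − 3)/(N − 4), where the last factor is the cost of estimating the slope.
- Ratio, ANCOVA to change score: (1 + r)/2 × (N − 3)/(N − 4).
- Example, r = 0.5 and N = 20: 0.75 × 17/16 = 0.80.
- Break-even r: 2(N − 4)/(N − 3) − 1.

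| n per arm | factor | r = 0.5 | r = 0.7 | break-even r |
|---|---|---|---|---|
| 35 | 1.015 | 0.76 | 0.86 | 0.97 |
| 20 | 1.028 | 0.77 | 0.87 | 0.95 |
| 10 | 1.0625 | 0.80 | 0.90 | 0.88 |
| 8 | 1.083 | 0.81 | 0.92 | 0.85 |
| 6 | 1.125 | 0.84 | 0.96 | 0.78 |

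Simulation with 20,000 trials per cell agrees with these ratios. It puts type I error near 5% for both tests.

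**Step 3: unequal SDs.** With s = post SD / pre SD, the ratio is (1 − r²)s² / (1 + s² − 2rs) × (N − 3)/(N − 4). At s = 1.25 and r = 0.7 the first part is 0.51 × 1.5625 / 0.8125 = 0.981. Multiplied by the factor this gives 1.01 at 20 per arm, 1.04 at 10 and 1.10 at 6. Break-even r falls to 0.68, 0.60 and 0.49. At s = 0.8 and r = 0.7 the first part is 0.628, which favours ANCOVA. The first part can never exceed 1, because its denominator minus its numerator is (1 − rs)². The loss is therefore capped by the factor: 2.8% at 20 per arm, 6.25% at 10 and 12.5% at 6.

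**Step 4: power, equal SDs, t-test then ANCOVA (noncentral t).**

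| n per arm | r = 0.5 | r = 0.7 |
|---|---|---|
| 28 | 45% → 56% | 66% → 72% |
| 16 | 28% → 34% | 42% → 47% |
| 8 | 15.4% → 17.7% | 22.5% → 23.9% |
| 6 | 12.3% → 13.5% | 17.3% → 17.6% |

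**Step 5: chance baseline imbalance.** The change-score contrast carries (1 − r) times any baseline difference between arms. Since 2(1 − r) = (1 − r²) + (1 − r)², this term is exactly the excess variance of Step 2. It explains that loss and adds nothing to it.

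**The case against.** The strongest reply is that this is a choice between two valid methods. The t-test is unbiased over randomisations, its type I error is unaffected, the protocol had already listed change scores, and Step 1 shows that the test matches the planned interaction. All of this stands. A reader might infer that the SAP's analysis is biased, or that it abandons the planned model for a weaker one; the documents support neither. Nor does the SAP claim that change scores gain precision. Its reference to small N may mean only a simpler plan.

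Second, no gain can be demonstrated from the documents. They give no pre-post correlation for any cognitive outcome, and the quoted POMS and BDI-II retest values lie above 0.5. The achieved N is unknown, and where it is smallest the gain is smallest. Step 3 shows that a modest rise in post-treatment SD can reverse it in small cohorts. This also stands, and it limits the claim to a conditional one.

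Third, a reader might count sensitivity to baseline imbalance as a separate harm, or suppose that an imbalance occurred. Step 5 answers the first. On the second, no imbalance is documented, and section 7.2.a balances allocation on age and cognitive screening score "so as to prevent different average ages or cognitive status scores between the treatment groups", which gives each outcome's own baseline some indirect protection.

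Fourth, d reported with a change-score t-test is most naturally read as using the pooled change-score SD, and nothing suggests that SDs were mixed across measures. Naming the SD is a clarification and adds no precision.

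What survives is narrow: neither document adjusts for the outcome's own baseline, and doing so is cheap.

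**Conclusion.** The point holds as an efficiency improvement, minor to moderate in weight. With equal SDs and r between 0.5 and 0.7, ANCOVA would cut the variance of the treatment contrast by 24% to 14% at 35 per arm, 23% to 13% at 20, 20% to 10% at 10 and 16% to 4% at 6. In power terms that is useful at 16 to 28 per arm and no more than about 2 points at 6 to 8. In small cohorts it can become a loss when r is high or the post SD is above the pre SD: 4% at 10 per arm and 10% at 6 in the case worked. A post SD below the pre SD favours ANCOVA.

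These sizes rest on assumed values of r, of the SD ratio and of the analysed N. The mood-scale retest figures are only proxies for the cognitive outcomes. The SAP's t-tests remain a valid analysis.

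**What to change.** Within each cohort, as section 7.3 already separates them, add an ANCOVA of post score on treatment and that outcome's baseline score. Report the adjusted difference with a 95% CI beside the change-score t-test. The SAP is written in the past tense, so label the ANCOVA as added after the original analysis. Use the baseline score as the only covariate by default.

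As accompanying reporting, state the SD used for Cohen's d (the same one for every measure), whether the t-tests are pooled or Welch, and the analysed N per arm.

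The cost is a few lines of SAP text, a re-run on data already collected, one degree of freedom per model, and a second labelled result per outcome. In the smallest cohorts there may be some loss of precision, capped as in Step 3. Showing both results side by side lets the reader see where that happens.
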